Data Management and Analysis. The qualitative study design and analysis follow the consolidated criteria for reporting qualitative research COREQ guidelines.¹⁵⁴ Focus group interview recordings will be transcribed professionally along with researcher notes describing participant behaviors and tone. Transcripts will be reviewed with the recordings for accuracy. We will use Dedoose (dedoose.com) secure, on-line qualitative data management program to manage the data. Initial data coding of the focus group transcripts and notes will be conducted by Drs. [name] and [name] using basic qualitative description and constant comparative techniques.¹⁵⁵⁻¹⁵⁷ Coding and analysis will be initiated after the first focus group and continue during subsequent focus group data collection. Portions of text will be labeled or coded with terms that are low inference (“data close”) and descriptive of participant words.¹⁵⁸ Codes will be grouped into thematic categories, and subcategories. All transcripts will be dual coded by [name] and [name] where codes and categories will be defined and coding discrepancies will be resolved during weekly analytic meetings. We will identify relationships between categories. Analytic procedures will include writing individual case (unit) summaries and thematic summaries, constructing stem-leaf plots to assess strength and distribution of themes across cases (units) and unit categories (high vs low-performing), identifying properties of themes and subthemes and creating visual hierarchical or relational diagrams. We will compare and contrast high and low bundle performing units through dimensional analysis and by constructing matrices.¹⁵⁹ Organizational Survey data will be categorically displayed and selected data from the Organizational Survey, such as unit characteristics, rounding practices, and ICU liberation bundle practices crossed with primary themes in a matrix analysis. Drs. [name] and [name] will share the analysis of the first four focus groups with the larger DISCOVER group investigators to elicit their input on additional analytic directions, alternate interpretations of focus group data and recommendations for other information to be elicited in the remaining focus groups. Key focus group participants will be selected to provide feedback on initial findings; their feedback will be incorporated into the final analytic product. As a final step, we will subject the focus group thematic categories and subcategories to traditional qualitative concept mapping⁴⁵ to identify relationships and potentially actionable intervention points in micro-decision processes to improve implementation of SATs, SBTs, and early mobility/exercise with MV patients.

Potential Problems and Alternative Approaches and Benchmarks for Success

Potential limitations of Aims 1 and 2 include the possibility of missing data and the large number of data elements to be analyzed. Our team has intimate knowledge of the database and the key measures we are using. We have collapsed the data into relatively broad categories based on the constructs/domains of the CFIR and will continue to refine these measures using the experience of the entire team. Should we find key elements missing, our continued relationship with the Collaborative sites will allow us to explore additional methods of addressing these limitations. While we have a rigorous plan to adjust for patient case mix in deriving ICU-level risk-adjusted bundle adoption rates, there will admittedly be unmeasured confounders (e.g., patient or caregiver preference) that may bias the ICU-level estimate. However, it is reasonable to expect that such unmeasured confounders will be distributed evenly across ICUs. Finally, there may be concern regarding our ability to recruit the necessary participants to complete the work proposed in Aims 3 and 4. As demonstrated in the sample **letters of support**, Collaborative members remain tremendously excited and committed to furthering the important work of bundle adoption.

Potential Pitfalls foreseen for Aim 4 are due to selection of high and low performing units for focus group participation will be based on data collected in 2015-2017, therefore unit characteristics may have changed and unit adherence may have improved or regressed since the data were collected. We also recognize that ICU environments and experiences in the care of mechanically ventilated patients are rapidly changing in response

to the COVID19 pandemic. This reality makes the addition of this micro-ethics study aim even more important as it will provide relevant context for the DISCOVER ICU study data integration and interpretation. Interprofessional team members may be reluctant to fully disclose ethical concerns in group interviews with other team members. Our experience has been that when techniques to engender social comfort are used and the discussion focuses on patient stories, interprofessional workgroups “open up.” Participation in focus group interviews may be low. We will employ the following strategies to boost participation in focus groups: 1) we will offer an incentive to each unit of \$50 dollar Amazon gift card to each focus group participant (payment will occur once the focus group is completed) and 2) we will offer each group a 1-year subscription to online communication training and toolkit in techniques to improve patient-provider communication. The SCCM connection and membership in the ICU Liberation Collaborative provide added motivation and incentive to participate. We expect that we will be successful in recruiting 10 units to participate in focus groups.

Expected Outcomes and Future Directions

The bioethics of implementation research is in its infancy. While patient engagement in implementation research has been discussed, little evidence exists about the process individuals undertake to elicit patient preferences, negotiate conflicts or include patient responses to bedside care with mechanically ventilated patients in the ICU. The need to optimize patient recovery following treatment with MV while minimizing provider burden has never been more important as the COVID-19 pandemic dramatically increases the number of adults of all ages who will experience an ICU admission and MV treatment. Future research could be directed at enhancing patient engagement with everyday micro-decisions to improve implementation of SATs, SBTs and early mobility/exercise. An additional research direction will be to determine if improved communication and patient engagement improves bundle performance and/or decreases moral distress of caregivers.

Study Timeline for Aim 1-4

Year	1				2				3			
Quarter	1	2	3	4	1	2	3	4	1	2	3	4
Submit IRB, recruit, hire, and train study personnel	X	X										
Study team in-person meetings		X				X				X		
Data extraction and cleaning Aim 1 and 2	X	X	X	X								
Data analysis Aim 1 and 2					X	X	X	X				

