Our preliminary data also show that collaborative participation resulted in significant but highly variable ABCDEF bundle adoption. Our next goal was to determine if collaborative participation led to increased bundle adoption. We were interested in exploring if some sites were "better" ABCDEF bundle adopters than others. The presence of a substantial amount of variability in our data would present us the opportunity to learn both from high- and low-bundle-performing sites. We calculated monthly rates of complete bundle performance, proportional bundle performance, and element-specific performance for the 17,258 patients across 49,109 full ICU days. We used segmented regression analysis for interrupted time series data to model the linear trend of bundle performance rates as a function of time for each segment (1-6 months pre-Collaborative involvement and 7-20 months during the Collaborative).

Complete bundle performance levels were low in the baseline (pre-Collaborative) period (i.e., < 4%). Complete bundle performance increased 2.0% (SE = 0.9%, $P = 0.057$) immediately after joining the Collaborative, and each month was associated with 0.6% greater increase (SE = 0.2%, $P = 0.038$) in complete bundle performance rates, compared to a relatively flat trend in the pre-Collaborative period. Proportional bundle performance rates also significantly increased by 3.8% (SE = 1.6%, $P = 0.026$) immediately after joining the Collaborative, then increased monthly at the same speed as the trend in the pre-Collaborative period (2%, SE = 0.4%, $P = 0.57$).

Bundle performance was highly variable among ICUs and across individual bundle elements; interquartile ranges of > 20% existed for all performance measures. (**Figure 1**) Elements A, C, D, and F were performed on average $\geq 70\%$ of the time at the end of the Collaborative:

Figure 1. Variation among ICUs in Unadjusted ABCDEF Bundle Performance Rates

adoption of elements B1, B2, and E (SATs, SBTs, and early mobility) proved far more challenging. For example, at the end of the Collaborative, an average $\leq 40\%$ of patients participated in early mobility and less than half of patients requiring MV received a daily SBT. Although overall performance was relatively poor, there were indeed some very good bundle performers.

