Setting and Sample. **Included** in the Collaborative were adults who were (1) initially admitted to a participating ICU and (2) designated as needing ICU level of care. Patients previously admitted to a non-participating ICU during their current hospitalization were not included. “ICU level of care” was defined as patients who (1) needed intensive medical and/or nursing care that not could not be delivered in a step-down and/or medical/surgical unit, (2) were managed by an ICU team, or (3) did not have transfer orders written or downgraded to a lower level of care. **Excluded** were patients who (1) died or were discharged within 24 hours of ICU admission or (2) were undergoing life support withdrawal and/or documented comfort care only within 24 hours of ICU admission.

Aim 1 data consist of **15,226** patients who spent 24 hours in a participating ICU (~**49,000 ICU patient-days**). Our sample includes patients on and off MV, ranging from 18-90+ years old, admitted with a variety of diagnoses. Of the 15,226 patients, 63% (n = 9619) were hospitalized in academic medical centers and admitted to mixed medical/surgical (56%), medical (18%), surgical/trauma (12%), neurologic (5%), or cardiac/surgical (10%) ICUs.

Procedures and Data Sources. The Vanderbilt University Medical Center Institutional Review Board (IRB) served as the Coordinating Center IRB and approved the SCCM ICU Liberation Collaborative QI project. All Collaborative participants acquired site-specific IRB evaluation and approval. No identifiable data were collected. All data were collected by standardized medical record review and anonymous staff surveys and were managed using a secure, web-based application designed for validated data entry, transmission, and storage (Research Electronic Data Capture [REDCap], Vanderbilt University, 2016 - grant support [(UL1 TR000445 from NCATS/NIH]).

[figure not shown]

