Local staff who attended a training webinar and as-needed support from SCCM managers entered de-identified data into the collaborative database at their individual hospitals. Data were collected retrospectively during a 6-month baseline period (January 2015-June 2015) and prospectively during a 14-month implementation period (January 2016-March 2017). During the baseline (pre-Collaborative) period, staff from each site entered data on the first 5 consecutively admitted ICU patients each month (30 baseline patients per site). Throughout the implementation period, site staff collected data on the first 15 consecutively admitted patients per month. For each patient, daily data were collected for a maximum of seven ICU days (average of 3.3 ICU-days per patient) or until patients transferred out of the ICU, were designated non-ICU status, or died.

Measures. Patient-level variables include: age, sex, race, ethnicity, language, body mass index (BMI), admitting diagnosis, severity of illness, and preadmission residence and mobility status. The severity of illness scores collected in the Collaborative included the Acute Physiology and Chronic Health Evaluation (APACHE) II,¹³⁰ APACHE III,¹³¹ and APACHE IV¹³² referent to the patient's status at the time of ICU admission.

Data analysis. We will conduct similar analyses for each of the performance measures (performed vs. not performed), including complete, proportional, and each element performance. We will first use descriptive statistics to examine data distribution, check for outliers, and summarize patient characteristics. Bivariate tests (e.g., *t* test or Chi-square statistics) will be used to compare patient characteristics in the pre-Collaborative and Collaborative periods.

Using multilevel segmented logistic regression modeling for interrupted time series data, we can model the likelihood of bundle performance change over time, both before and during the periods of Collaborative implementation. **Figure 2** shows a hypothetical example. The basic form of the level-1 model (Figure x, solid black line) can be written as $\text{Logit}(Y_{ij}) = \beta_{0j} +$

Figure 2. Segmented logistic regression for ITS data-A hypothetical example

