β_{1j} Month + β_{2j} Imp + β_{3j} Month * Imp + e_{ij} , where (1) Logit(Y_{ij}) denotes the logit (or log-odds) of receiving bundle performance for the i^{th} ICU-day of the j^{th} patient; (2) Month is the month indicator of the study period (a total of 20 months coded as -5 to 0 for pre-implementation period and 1 to 14 for implementation period); and (3) Imp denotes an indicator variable coded as 0 for pre-implementation period and 1 for the implementation period. Therefore, Logit(Y_{ij}) is modeled as a linear function of $\beta_{0j} + \beta_{1j}$ Month for the pre-implementation period and $(\beta_{0j} + \beta_{2j}) + (\beta_{1j} + \beta_{3j})$ Month for the implementation period. β_{2j} and β_{3j} are the estimates of level and slope changes due to the intervention implementation. A significant level change (β_{2j}) indicates an immediate change in the level of bundle performance at the initiation of intervention implementation. A significant slope change (β_{3j}) indicates different trends over time during the pre- vs. post-implementation periods. Under the multilevel modeling framework, level-2 models will fit β_{0j} , β_{1j} , β_{2j} , and β_{3j} each as a linear function of fixed-effects of patient characteristics and patient-specific random effects. The patient-specific random terms allow for adjustment of within-patient clustering of ICU-days. Take patient gender as an example. From the combined multilevel segmented logistic regression model, we will (1) estimate the overall trends during the pre- and implementation periods (solid black lines); (2) derive fixed-effect estimates by patient characteristics (Figure 4, long dashed line and short dashed line for each gender); (3) test the significance of hypothesized subgroup differences (e.g., older age, obese, and non-English speaking) in the these estimates; and (4) include patient-specific random terms to allow for variability by patients (patient-specific lines not shown in Figure 4). The model can be simplified if supported by the preliminary results. For example, if the initial analyses for an outcome (e.g., element E performance) suggest that (1) there are no significant level change and slope change for both male and female patients and (2) the overall increasing trend over time does not differ by patient gender, we can reduce the model to a parsimonious form using multilevel logistic regression to model the probability of having an outcome as a function of fixed effect of patient gender, fixed effect of time, and patient-specific random effects. We can also further extend the model to (1) include multiple patient characteristics simultaneously in the model to generate multivariable adjusted estimates, (2) perform curve fitting for linear or non-linear trend, and (3) adjust for additional clustering (e.g., within-organization clustering). The above desried multilevel segmented logistic regression approach will be applied to analyzing complete and element bundle performance measures. For proportional bundle performance, we will use multilevel segmented Poisson regression instead.

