
Power analysis. We used the simulated-based power calculation method by Zhang et al.¹³³ for interrupted time series analysis to conduct power analysis for Aim 1. With the expected ~49,000 ICU-days of ~15,000 patients in 68 ICUs, we generated 1,000 simulations with various patient subgroup distributions and proportion of ICU days with bundle performance during the pre-implementation and implementation periods. Our preliminary analyses of the pre-implementation period data suggest that the probability of bundle performance ranged from 0.05 (for complete bundle performance) to 0.60 (for performance of element A) at the end of the pre-implementation period and a monthly increase in the probability ranged from zero (for element E) to 0.05 (for element D). To be conservative in power calculation, we used a probability of 0.05 for the level and a 0.05 monthly increase in the probability for the slope in the pre-implementation period. Our power analysis suggested that our data will have 80% power to detect an odds ratio (OR) of 1.25 (corresponding to an increase of 0.02 in the probability of receiving bundle performance) and 80% power to detect a slope change, with an OR of 1.52 corresponding to pre- vs. post-difference of 0.03 in the monthly increase of the probability of receiving bundle care. Based on our preliminary data, we reasonably assumed an autocorrelation of 0.5 under the first order auto-regressive covariance structure, a within-patient correlation of 0.5, and a within-hospital correlation of 0.6 in our simulation-based power calculation. Under the same assumptions, we also conducted power analyses on the effects of patient characteristics on the level and slope changes. For patient characteristics with 20:80 distribution, our sample size will have 80% power to detect an OR of 1.73 for the effect of patient characteristics on level change and 80% power to detect an OR of 2.65 for the effect of patient characteristic on slope change. The above power calculation is the most conservative scenario. The study power will be greater than 80% for other cases (e.g., pre-probability of 0.5, patient characteristics with 50:50 distribution). Regardless of study power, we will report point estimates, 95% confidence intervals, and use clinical significance to guide results interpretation. All above calculations were based on multilevel segmented logistic regression with a 0.05 two-sided significance level and adjusted for data dependencies described above.

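### The monthly patient quota changes from 5 to 15 exactly where the implementation period begins, and the plan has no admission-order term or common-quota check on the overall level change

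*Combined protocol and SAP*

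**What the plan says.** Under Aim 1, Procedures and Data Sources, the baseline rule is that "staff from each site entered data on the first 5 consecutively admitted ICU patients each month (30 baseline patients per site"). For the implementation period, "site staff collected data on the first 15 consecutively admitted patients per month". The same paragraph gives the calendar and the mode of collection: "Data were collected retrospectively during a 6-month baseline period (January 2015-June 2015) and prospectively during a 14-month implementation period (January 2016-March 2017").

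The Aim 1 Data analysis section sets out a segmented logistic model. Its basic level-1 form contains Month, Imp (0 before, 1 during implementation) and their product. At level 2, each coefficient may depend on patient characteristics and patient random effects. Of the coefficients for Imp and the product, the section says that they "are the estimates of level and slope changes due to the intervention implementation". Bivariate tests will compare patient characteristics between the two periods. Joint adjustment for several characteristics, and for clustering above the patient, is offered as a possible extension.

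Aim 2 reuses the model with ICU random effects and keeps the significant patient characteristics as covariates. Aims 2 and 3 then model organizational characteristics and implementation strategies as effects on the level and slope changes. No section mentions admission order within the month or an analysis on a common quota.

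**The concern.** In an interrupted time series, the level change absorbs anything that changes at the boundary. Here the rule for entering the sample changes there. Ten of every 15 implementation patients (admissions 6-15) belong to a group that was not sampled at baseline. If bundle performance in that group differs from performance in the first five admissions, for instance through unmeasured case mix, staffing or timing, the difference is counted as part of the effect of joining the Collaborative. A larger sample does not reduce it.

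The effects under study are small enough for this to be worth a check. The Aim 1 Power analysis is built around a level-change odds ratio of 1.25, or 0.02 in probability. The Preliminary Data section reports a level change in complete bundle performance of 2.0 points (SE 0.9).

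**Working it through.** **Inputs.** Quotas of 5 and 15 per ICU-month, 6 and 14 months (Aim 1, Procedures and Data Sources); months coded -5 to 0 and 1 to 14 (Aim 1, Data analysis); 68 ICUs and a baseline probability of 0.05 (Aim 1, Power analysis); level change 2.0 points, SE 0.9 (Preliminary Data). The order effect d is not in the documents, so a range is shown.

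**1. The plan's own figure.** 5 × 6 = 30 baseline patients per site, as stated. With filled quotas, baseline has 68 × 30 = 2,040 patients and implementation 68 × 15 × 14 = 14,280.

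**2. Bias on the linear scale.** Let admissions 6-15 perform d points better than admissions 1-5, with no true change at the boundary.
- Every baseline month has mean μ.
- Every implementation month has mean (5μ + 10(μ + d))/15 = μ + 0.667d.
- The shift is constant within each period, so the level change is biased by 0.667d and the slope change by 0. Least squares on the stated schedule returns the same values.

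Against the preliminary 2.0 points (SE 0.9):

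| d (points, assumed) | bias = 0.667d | bias / 0.9 |
|---|---|---|
| 0 | 0 | 0 |
| 0.5 | 0.33 | 0.4 |
| 1 | 0.67 | 0.7 |
| 2 | 1.33 | 1.5 |

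That SE comes from a segmented regression of monthly rates, not from the planned multilevel logistic model, so the last column gives scale only.

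**3. Bias on the logistic scale.** Take probability 0.05 (odds 0.0526) in admissions 1-5 and an assumed order odds ratio R.
- R = 1.1: later admissions 0.0547; mixture (0.05 + 2 × 0.0547)/3 = 0.0532; spurious level odds ratio 1.07.
- R = 1.2: later admissions 0.0594; mixture 0.0563; spurious odds ratio 1.13.
- R = 1.4: later admissions 0.0686; mixture 0.0624; spurious odds ratio 1.26.

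An order odds ratio of about 1.4 would therefore be needed to imitate the detectable 1.25.

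**4. Precision cost of the two remedies.** Per ICU, independent patients, unit variance. The level change is the difference between the two fitted lines at Month 0.
- Baseline line: 1/30 + 2.5²/(5 × 17.5) = 0.0333 + 0.0714 = 0.1048.
- Implementation line, 15 per month: 1/210 + 7.5²/(15 × 227.5) = 0.0048 + 0.0165 = 0.0212. Total 0.1260.
- First 5 only: 1/70 + 7.5²/(5 × 227.5) = 0.0143 + 0.0495 = 0.0637. Total 0.1685. SE ratio √(0.1685/0.1260) = 1.16.
- Order indicator: var(d) = 1/70 + 1/140 = 0.0214; total 0.1260 + 0.667² × 0.0214 = 0.1355. SE ratio √(0.1355/0.1260) = 1.04.
- Slope change: 1/87.5 + 1/3412.5 = 0.01172 for all patients and 1/87.5 + 1/1137.5 = 0.01231 for the first 5; SE ratio 1.02. With the indicator the ratio is 1.00.

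Taking the plan's 80% power at an odds ratio of 1.25 as given:
- First 5 only: power Φ(2.80/1.156 - 1.96) = 68%; detectable odds ratio exp(1.156 × ln 1.25) = 1.29.
- Order indicator: power Φ(2.80/1.037 - 1.96) = 77%; detectable odds ratio exp(1.037 × ln 1.25) = 1.26.

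**5. Are the quotas exactly filled?** Not on the stated schedule. It allows at most 2,040 + 14,280 = 16,320 patients, whereas the preliminary series has "17,258 patients across 49,109 full ICU days". The calendar dates given for implementation span 15 months rather than 14; over 15 months the maximum is 2,040 + 68 × 15 × 15 = 17,340. With filled quotas the factor 0.667 is the same for 14 or 15 months. With uneven filling, neither 0.667 nor the zero slope bias is exact.

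**The case against.** The strongest reply is that the baseline quota is nested in the implementation quota. Both take consecutive admissions from the start of the month under the same eligibility criteria, so a larger quota alone changes precision and not the expected value. Bias needs an order effect, and the documents show none. They give no monthly admission volumes, so it is not established that admissions 6-15 come from a distinctly later part of the month. The outcome is recorded by ICU-day for up to seven days, so the two groups can overlap in calendar time. This stands, and it is why d = 0 belongs in the range.

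Measured case mix is also not ignored. Patient characteristics can enter the baseline level and the level change at level 2, and Aim 2 keeps the significant ones. This stands for measured characteristics. It does not cover admission order, staffing or timing, and joint adjustment is optional in Aim 1.

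The large values of d are implausible for complete bundle performance, which was below 4% at baseline. If the early implementation average were 6% (assumed), d = 2 points would mean about 4.7% against 6.7%, an odds ratio of about 1.46 from order alone; d = 3 would mean 4% against 7%, about 1.81. A reader might infer that the preliminary 2.0-point change is an artefact of sampling. The documents do not support this: it would need d = 3.

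A reader might also infer that the patient, organization and strategy effects, which are the targets of Aims 1 to 3, are biased in the same way. They are not. An order effect common to all groups cancels from a difference in level change, and the documents give no reason to expect it to vary by group. Aim 2's ICU rankings use adjusted rates from the last implementation month, when every ICU follows the same quota.

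Finally, admission order and date are not among the listed patient variables, so the order indicator may not be possible.

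**Conclusion.** The point holds in a limited form. The quota changes at the same boundary as Imp, and the plan has neither an order term nor a common-quota check. The overall level change would carry a bias of about 0.67d, and the slope change none, assuming filled quotas, an additive order effect that is constant over time, and similar numbers of ICU-days per patient in both order groups. The size of d is unknown and may be zero, so this is a comparability check that the plan should make, not a demonstrated bias. Differences in level change by patient, organization or strategy are at risk only if d differs across those groups.

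Attributing the level change to implementation is stronger than the design allows whatever the value of d. Baseline data are retrospective and implementation data prospective, and July to December 2015 is missing between them. Both features load on the same coefficient, and no adjustment for admission order removes them.

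**What to change.** In the Aim 1 Data analysis section:

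- Pre-specify a sensitivity analysis of the same segmented model restricted to the first 5 patients per ICU-month in both periods. Cost, ignoring clustering: level-change SE about 16% larger, slope-change SE about 2% larger.
- Where admission or entry order can be recovered, also fit the full-data model with an indicator for 6th-15th versus 1st-5th, and report the estimated order effect with its confidence interval. Cost: level-change SE about 4% larger, slope-change SE unchanged. State which order was used, since entry order need not equal admission order.
- Carry both analyses into the level-change models of Aims 2 and 3. There, the quantity to examine is whether the order effect differs by organizational characteristic or strategy.
- If neither order can be recovered, neither analysis can be run; state the differing quotas as a limitation of the overall level change.
- In every case, describe the level change as the change at the start of the implementation period. Name the change in mode of collection and the six-month gap as alternative explanations that these analyses do not address.

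No new data collection is needed. The work is one extra run and, if order exists in the records, one covariate.
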